5.7.4.3 Comparative analyses

Internal comparator analysis

Only prospective pregnancies will be included in the internal comparator analysis. As described in Section 5.7.1.3 in the primary analysis of major congenital malformations, Cohort A will be compared to Cohort B1. In a secondary analysis of major congenital malformations, Cohort A will be compared to Cohort B overall and Cohort B2. All secondary outcome proportions in Cohort A will be compared to Cohort B, as well as separately with Cohorts B1 and B2 using the risk ratio (one-sided 97.5% CIs). The difference in proportions will also be compared to the defined clinical equivalence margin to reject the hypothesis that the rate in Cohort A is higher than in Cohort B1. Also, comparisons may be explored using risk ratios adjusted to relevant covariates through methods such as propensity score weighting, if the sample size is sufficient in subgroups of the covariates. The key covariates of interest that will be considered for adjustment are maternal age, prior history of elective or therapeutic pregnancy termination status, other

Confidential

insomnia treatment exposures, and baseline alcohol, smoking, marijuana, and drug use. Other prior pregnancy and prior infant outcomes will be explored and considered for adjustment at the time of analysis.

The primary and secondary outcomes will be evaluated and described among subgroups of patients defined by key characteristics of interest including maternal age, race/ethnicity, smoking, and exposure to other insomnia medications [see Section 5.7.4.4].

External comparator cohort analysis

Prevalence for major congenital malformations in Cohort A will be assessed in parallel to the prevalence observed in available external comparator cohort(s) representing the background prevalence of birth defects in the general US and EEA population. The MACDP and EUROCAT classification of congenital malformations will be implemented to ensure comparability to US and EEA populations, respectively.

Categorical distributions available in the MACDP will be summarized using the same categories among the QUVIVIQ-exposed pregnancies. Indirect standardization methods will be applied for categorical distributions of maternal age, gestational age, and race/ethnicity. Indirect standardization involves calculating the observed number of events (i.e., major congenital malformations) and applying the maternal age, gestational age, and race/ethnicity distributions from the reference population (i.e., MACDP and EUROCAT) to calculate the expected number of major congenital malformations. The ratio of the observed number of major congenital malformations to the expected number of major congenital malformations is referred to as the standardized prevalence ratio.

Adjusted prevalence can be calculated by multiplying the standardized prevalence ratio by the crude congenital malformation rate.

It is important to emphasize that any external comparator data source and women enrolled in this study are 2 distinctly different datasets, thus "external adjustment methods" for inference comparisons are limited.

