OUTCOMES	Primary outcome measure
	Occurrence of major congenital malformations.
	Secondary outcome measures
	Minor congenital malformations.
	 Complications during pregnancy (preeclampsia, pregnancy-induced hypertension, preterm labor, gestational diabetes).
	• Spontaneous abortion (loss of fetus due to natural causes< 20 weeks gestation).
	• Fetal death or stillbirth (death of a fetus prior to birth or after 20 weeks of gestation).
	• Preterm birth (< 37 weeks gestation).
	• Full-term live birth, i.e., infants born maturely (≥ 37 weeks gestation).
	• Elective termination, i.e., any induced or voluntary fetal loss.
	• Small for gestational age at birth (birth weight < 10 th percentile).
	Any other adverse pregnancy outcomes.
	• Infant mortality (up to the first year of life).
	• Infant hospitalizations for serious illness (up to the first year of life).
	Postnatal growth and development (i.e., social/emotional, language/communication, neurocognitive, movement/physical development milestones) up to the first year of life.
STATISTICAL ANALYSIS	Retrospective pregnancies will be analyzed in a separate case series with respect to demographic and clinical information and QUVIVIQ exposure (e.g., timing of exposure and duration). In addition, all reported primary and secondary outcomes will be assessed.

Confidential

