5.5 Study size

5.5.1 Sample size calculation for the primary outcome

The sample size (i.e., the number of enrolled patients) was calculated to ensure sufficient power to compare the prevalence of major congenital malformations in the infants of women exposed to QUVIVIQ (Cohort A) with infants of women exposed to other non-ORA medications for insomnia (Cohort B1) in the primary analysis using an NI testing approach with a one-sided significance level of $\alpha = 0.025$.

Hypothesis:

```
H_0: P_A- P_{B1} > margin versus H_1: P_A- P_{B1} < margin
```

where

P_A is the probability of major congenital malformations in Cohort A.

P_{B1} is the probability of major congenital malformations in Cohort B1.

The null hypothesis is that P_A is larger than P_{B1} by a margin corresponding to a risk ratio of 3.0:

```
Risk Ratio = (P_{B1} + margin) / P_{B1}
or margin = P_{B1}*Risk Ratio -P_{B1}
```

A general population prevalence of major congenital malformations of 3% among women in Cohort B1 is assumed. The NI margin is 3%*3.0–3%=6%.

Assuming a true difference of 0.15% between P_A and P_{B1} (corresponding to a relative increase of 5% from P_{B1}), sample sizes of 102 pregnancy outcomes in Cohort A and 204 events in Cohort B1 achieve 80.1% power to exclude an increase in risk of more than a risk ratio of 3 in Cohort A compared to Cohort B1. The test statistic used is the one-sided Z-test with a significance level of 2.5%. The proportion for the reference group is $P_{B1} = 3\%$

[see Table 3]. Calculations were made by using nQuery V9.1.1.0, module PTE0U-1 [Machin 1987].

The hypothesis testing will be based on comparing the upper bound of the 97.5% one-sided confidence interval for P_{A^-} P_{B1} with the NI margin. If the upper bound is below the NI margin, then noninferiority of A vs B1 will be concluded.

The following formula was utilized to calculate sample size:

$$Na = \frac{(r+1) * (Z_{1-\beta} + Z_{1-\alpha})^{2} * (\frac{Pa * (1-Pa) + Pb1 * (1-Pb1)}{2})}{r * ((Pa - Pb1) - margin)^{2}}$$

$$Nb1 = r * Na$$

where N_A is the number of pregnancy outcomes required in Cohort A, N_{B1} is the number of pregnancy outcomes required in Cohort B1, r is the allocation ratio (Cohort A: Cohort B1, 1:2 ratio), $Z_{1-\beta}$ and $Z_{1-\alpha}$ are the 80% and 97.5% percentiles of the standard normal distribution, respectively.

Sample size estimates with risk ratios varying from 2.0 to 3.0 and with various observed percentages in Cohort A are presented in Table 3.

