Infant outcomes	Minor congenital malformations ^m	2.0%		3	4.0%	62.5%	50.2%	67.8%
	mariormations			3.5	5.00%	81.7%	69.5%	86.1%
	Small for gestational age ⁿ	10.0%	10.50%	2.5	15.0%	97.7%	92.7%	98.8%
Infant outcomes				3	20.0%	> 99.9%	> 99.9%	> 99.9%
				3.5	25.00%	> 99.9%	> 99.9%	> 99.9%
	Low birth weight ^o	8.5%	8.93%	2.5	12.8%	95.1%	87.7%	97.0%
Infant outcomes				3	17.0%	> 99.9%	98.7%	> 99.9%
				3.5	21.25%	> 99.9%	> 99.9%	> 99.9%
	Infant death ^p	2.9%	3.05%	2.5	4.4%	53.5%	42.3%	58.5%
Infant outcomes				3	5.8%	78.6%	66.1%	83.3%
				3.5	7.25%	93.3%	84.7%	95.7%
	TT '. 1' .'	2.0%	2.10%	2.5	3.0%	39.5%	30.9%	43.7%
Infant outcomes	Hospitalizations for serious illness ^q			3	4.0%	62.5%	50.2%	67.8%
				3.5	5.00%	81.7%	69.5%	86.1%

Confidential

23 October 2023, page 48/90

Secondary outcome category ^a	Secondary outcome ^b	P _B (B, B1 and B2)	P _A ^c	Risk ratio	NI margin	Power for A vs B1	Power for A vs B2	Power for A vs B
	Postnatal growth and development ^{c,r}	6.0%	6.30%	2.5	9.0%	85.0%	73.4%	89.0%
Infant outcomes				3	12.0%	98.1%	93.6%	99.0%
				3.5	15.00%	> 99.9%	> 99.9%	> 99.9%

^a The total population of enrolled patients (n = 785) was used to estimate the power for the secondary outcomes in the pregnancy complications and pregnancy outcomes categories. The number of pregnancy outcomes (n = 408) was used to estimate the power for the secondary outcomes in the infant outcomes category.

NI = non-inferiority; $P_A = prevalence$ in Cohort A; $P_B = prevalence$ in Cohort B.

^b Only live births were considered positive outcomes. All other outcomes were considered negative. Because the assumed rate of live birth in Cohort B is high (62%), the estimated rate of live birth in Cohort A for risk ratios of 2.5 or higher corresponds to a rate below 0%, which is not realistic. Therefore, the estimated power is >99.9%.

^c For negative outcomes, the assumed prevalence in Cohort A is $P_A = 1.05 \cdot P_B$. For positive outcomes, the assumed prevalence is $P_A = 1 - ((1 - P_B) \cdot 1.05)$.

d Source data: [Abalos 2013]

^e Source data: [Turner 2017]

f Source data: [Danforth 2008]

g Source data: [Behboudi-Gandevani 2019]

h Source data: [Jones 2017]

ⁱ Source data: [Ammon Avalos 2012]

^j Source data: [Hug 2021]

k Source data: [Ventura 2000]

¹ Source data: [Walani 2020]

^m Source data: [Chimah 2022]

ⁿ Source data: [Sclaudecker 2017]

Source data. [Sciaduceker 2017

^o Source data: [Osterman 2023]

p Source data: [who.int]

^q Source data: [McLaughin 2022]

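### Section 5.7.4.3 tests every secondary outcome for a higher rate in Cohort A, so the live-birth comparison cannot show harm, and this contradicts Table 4's own treatment of live birth as a favourable outcome

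*Protocol*

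**What the plan says.** Section 5.7.4.3 (internal comparator analysis) says "All secondary outcome proportions in Cohort A will be compared to Cohort B, as well as separately with Cohorts B1 and B2". The measure there is a risk ratio with one-sided 97.5% intervals. The next sentence compares the difference in proportions with a margin "to reject the hypothesis that the rate in Cohort A is higher than in Cohort B1". No outcome is excepted and no other direction is given.

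The one decision rule written out in full is for the primary outcome, in Section 5.5.1: "If the upper bound is below the NI margin, then noninferiority of A vs B1 will be concluded". It uses the upper bound of P_A − P_B1.

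Two secondary outcomes are favourable events. Live birth is in Table 4 and Appendix 4. The synopsis lists "Full-term live birth, i.e., infants born maturely" among the secondary outcome measures.

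Table 4 treats live birth differently from the rest. Its footnote b says "Only live births were considered positive outcomes. All other outcomes were considered negative". Footnote c sets the assumed Cohort A rate for a positive outcome below the Cohort B rate. Footnote b also reads the margin downward, noting that it would take the Cohort A rate below zero. Full-term live birth has no row, rate or margin in Table 4.

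**The concern.** For malformations, losses, preterm birth and the like, a higher rate in Cohort A is the harm, and an upper-bound rule asks the safety question. For live birth and full-term live birth the harm is a lower rate. Ruling out a higher rate then says nothing about safety.

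Section 5.5.2 powers live birth for a decrease, while Section 5.7.4.3 tests for an increase. If the analysis text is followed, a marked fall in live births in a safety registry could be reported as having met its criterion.

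**Working it through.** **Inputs.** Live birth rate in Cohort B: 62% (Table 4). Women enrolled: 204 in A and 387 in B1 (Section 5.5.1), the numbers Table 4 uses for pregnancy outcomes. One-sided α = 0.025. Margin formula in Section 5.5.1: P_B × RR − P_B. Margins of 6, 10 and 15 points for live birth are my assumptions; the protocol sets no attainable margin for it.

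**1. The plan's own figures.** Primary outcome: P_A = 3.15%, P_B1 = 3%, margin 6 points, r = 2.
- Average variance = (0.0315 × 0.9685 + 0.03 × 0.97)/2 = 0.02980.
- N_A = (3/2) × (0.8416 + 1.9600)² × 0.02980 / (0.0015 − 0.06)² = 102.5 (stated: 102).
- Power at 102 and 204 = 79.8% (stated: 80.1%).

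Preeclampsia in Table 4 at RR 2.5, by the same method: 95.3% against B1 and 88.1% against B2 (stated: 95.5% and 88.4%). The method and sample sizes are therefore those of the plan.

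**2. Live birth as tabulated.** Footnote c gives P_A = 1 − 0.38 × 1.05 = 0.601, a decrease. The margins are 0.62 × 1.5 = 93 points, 0.62 × 2 = 124 points and 0.62 × 2.5 = 155 points. With B1 at 62%, A can exceed it by at most 100 − 62 = 38 points and fall below it by at most 62 points. The largest possible risk ratio is 1/0.62 = 1.61. None of the printed margins can be reached in either direction.

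**3. Chance that the rule passes.** Full binomial enumeration with P_B1 = 62%. Rule as written: d + 1.96 × SE < m. Reversed rule: d − 1.96 × SE > −m. Here d is the observed difference A − B1 and SE its unpooled standard error.

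| True rate in A | As written, m = 93 | As written, m = 6 | As written, m = 10 | Reversed, m = 93 | Reversed, m = 10 |
|---|---|---|---|---|---|
| 72% | 1.00 | 0.1% | 2% | 1.00 | 99.8% |
| 62% | 1.00 | 30% | 67% | 1.00 | 66% |
| 55% | 1.00 | 86% | 98% | 1.00 | 11% |
| 50% | 1.00 | 99% | 99.9% | 1.00 | 0.8% |
| 45% | 1.00 | >99.9% | 100% | 1.00 | <0.1% |

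With 15% attrition (173 and 329 women) the 6-point figures at 62, 55, 50 and 45% are 26%, 80%, 97% and 99.9%. A risk-ratio version, upper bound below 2.5 or 3, also passes with probability 1.00 at every rate from 72% down to 5%.

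**4. Does reversing the direction suffice?** No. The reversed rule at 93 points still always passes. Moving to the complement (no live birth, 38%) but keeping RR 2.5 gives a margin of 0.38 × 1.5 = 57 points. That rule still passes about 99% of the time when live births fall to 20%.

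**5. Full-term live birth.** The protocol gives no rate or margin, so nothing can be computed. The direction problem is the same.

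**The case against.** - **The margin sentence may not cover live birth.** It names only Cohort B1 and a single margin, so it could be read as describing the primary test. That ambiguity is real. But it directly follows the sentence on all secondary outcomes, and Table 4 gives non-inferiority margins outcome by outcome, which favours the wider reading. On the narrow reading the secondary intervals are still one-sided with no side stated, and upper is the only direction the hypothesis or analysis text gives.
- **The protocol already knows the direction, and the SAP can set the bound.** The footnotes do show the intent. That is why this is a contradiction between two sections and not an oversight throughout. The SAP is not at hand, but Section 5.7.4.3 does state a direction, and for these outcomes it is the wrong one.
- **A fall in live births would be visible elsewhere.** This stands. Spontaneous abortion, stillbirth, termination and preterm birth are separate secondary outcomes tested in the right direction, and prevalences are reported by cohort. It limits the damage but does not correct a wrong conclusion on live birth itself.
- **The stronger reading.** A reader might infer that the rule, as the protocol fixes it, passes more often the worse QUVIVIQ does, and that a true benefit would fail it. The documents do not support that. At the printed margins the pass probability is flat at 1.00. The rising pattern appears only at a margin the protocol never sets for live birth; its 6 points belong to malformations at a 3% baseline.

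**Conclusion.** The point holds as a contradiction between Sections 5.5.2 and 5.7.4.3 and as a rule that cannot detect harm for a favourable outcome. For live birth it passes with probability 1.00 at the printed 93, 124 and 155 points. At an assumed margin of 6 or 10 points it would pass more often as live births fall: 30% or 67% with no difference, 99% or 99.9% at a true rate of 50%. These figures assume 62% in B1, 204 and 387 women with known outcome, an unadjusted Wald interval, and the reading that the margin test applies to secondary outcomes. For full-term live birth only the missing direction, rate and margin can be stated. The primary analysis is untouched. The change should be made, but the point does not threaten the main conclusion.

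**What to change.** In Section 5.7.4.3, state that live birth and full-term live birth are analysed through their complements (no live birth; no full-term live birth) with the upper-bound rule. Equivalently, use the lower one-sided 97.5% bound of P_A − P_B for these two outcomes, with the null that Cohort A is lower by the margin or more. Say in the same place whether the margin test covers B1 only or also B2 and B.

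In Table 4, replace the live-birth margins with an attainable one on the chosen scale and restate the power. Give a rate and margin for full-term live birth, or remove it from the synopsis list if it is not meant to be tested.

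The cost is a short protocol edit and the recoding of two outcomes, with no new data or enrolment. The downside is that the stated live-birth power above 99.9% will fall. With P_A = 60.1%, 204 against 387 women and the lower-bound rule, it is about 17%, 49% and 87% at assumed margins of 6, 10 and 15 points.

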Risk ratio	Assumed prevalence in Cohort B1	Expected prevalence of MCM in Cohort A ^a	NI margin corresponding to the risk ratio	Cohort A with 15% attrition rate, 62% live birth rate, and 5% exposure to insomnia medications other than OUVIVIO	Cohort B1 with 15% attrition rate and 62%live birth rate
2.50	3.0%	3.0%	4.50%	340 (Pregnancy outcomes needed: 170)	643 (Pregnancy outcomes needed: 339)
2.50	3.0%	3.15%	4.50%	370 (Pregnancy outcomes needed: 185)	698 (Pregnancy outcomes needed: 368)
2.50	3.0%	3.3%	4.50%	401 (Pregnancy outcomes needed: 201)	761 (Pregnancy outcomes needed: 401)
2.25	3.0%	3.0%	3.75%	487 (Pregnancy outcomes needed: 244)	926 (Pregnancy outcomes needed: 488)
2.25	3.0%	3.15%	3.75%	537 (Pregnancy outcomes needed: 269)	1021 (Pregnancy outcomes needed: 538)
2.25	3.0%	3.3%	3.75%	595 (Pregnancy outcomes needed: 298)	1129 (Pregnancy outcomes needed: 595)
2.0	3.0%	3.0%	3.0%	761 (Pregnancy outcomes needed: 381)	1446 (Pregnancy outcomes needed: 762)
2.0	3.0%	3.15%	3.0%	857 (Pregnancy outcomes needed: 429)	1628 (Pregnancy outcomes needed: 858)
2.0	3.0%	3.3%	3.0%	971 (Pregnancy outcomes needed: 486)	1843 (Pregnancy outcomes needed: 971)

^a Expected prevalence in Cohort A is P_A = 1.0, 1.05, 1.10 · P_B, reflecting that the expected prevalence in Cohort A is slightly higher (increase of 0%, 5%, 10%) than the background prevalence in Cohort B.

MCM = major congenital malformation; NI = non-inferiority.

For the secondary analysis (comparison of the prevalence of major congenital malformations in the infants of Cohort A to the infants of Cohort B2), 194 pregnancy

Confidential

outcomes in Cohort B2 (1:1 ratio Cohort A:Cohort B2) would allow 86% power to rule out a difference represented by a risk ratio of 3.5 or higher in major congenital malformations at a significance level of $\alpha = 0.025$.

If the prevalence observed in Cohort A is lower than 3.15% (expected prevalence), there will be greater power to demonstrate that the rate of major congenital malformations in the infants of patients in Cohort A is not larger than in Cohort B1.

Subject recruitment will be evaluated at each interim review. Interim analyses are planned for the 5th year after the first patient enrolls, and annually thereafter [Section 5.1]. This will include a sample size re-estimation examining the observed prevalence and risk ratio of major congenital malformations in Cohort A compared with Cohort B1 and account for patient recruitment rates and enrollment projects.

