5.5.2 Power for secondary outcomes

785 total enrolled women with 408 pregnancy outcomes (102 for Cohort A, 204 for Cohort B1, and 102 for Cohort B2) will have the following power to rule out a difference represented by the risk ratios presented below [Table 4] for each of the secondary outcomes.

QUVIVIQ® (daridorexant) Insomnia disorder ID-078A403 Version 4 23 October 2023, page 46/90

Confidential

 Table 4
 Power estimates for secondary outcomes

Secondary outcome category ^a	Secondary outcome ^b	P _B (B, B1 and B2)	P _A ^c	Risk ratio	NI margin	Power for A vs B1	Power for A vs B2	Power for A vs B	
To the state of th		4.6%	4.83%	2.5	6.9%	95.5%	88.4%	97.4%	
Pregnancy complications	Preeclampsia ^d			3	9.2%	> 99.9%	98.8%	> 99.9%	
				3.5	11.50%	> 99.9%	>99.9%	> 99.9%	
D	II			2.5	4.5%	83.2%	71.0%	87.6%	
Pregnancy complications	Hypertensive disorders ^e	3.0%	3.15%	3	6.0%	97.6%	92.2%	98.7%	
	G 1551 G 51			3.5	7.50%	> 99.9%	98.9%	> 99.9%	
D			3.15%	2.5	4.5%	83.2%	71.0%	87.6%	
Pregnancy complications	Preterm labor ^f	3.0%		3	6.0%	97.6%	92.2%	98.7%	
				3.5	7.50%	> 99.9%	98.9%	> 99.9%	
n.		1 4.4%	4.62%	2.5	6.6%	94.6%	86.5%	96.7%	
Pregnancy complications	Gestational diabetes ^g			3	8.8%	> 99.9%	98.5%	> 99.9%	
complications	diabetes			3.5	11.00%	> 99.9%	>99.9%	> 99.9%	
	Elective or				2.5	27.0%	> 99.9%	>99.9%	> 99.9%
Pregnancy outcomes	therapeutic pregnancy	18.0%	18.90%	3	36.0%	> 99.9%	>99.9%	> 99.9%	
outcomes	terminations ^h			3.5	45.00%	> 99.9%	>99.9%	> 99.9%	
			11.55%	2.5	16.5%	> 99.9%	>99.9%	> 99.9%	
Pregnancy outcomes	Spontaneous abortions ⁱ	11.0%		3	22.0%	> 99.9%	>99.9%	> 99.9%	
outcomes				3.5	27.50%	> 99.9%	>99.9%	> 99.9%	
	Fetal death or stillbirth ^j	1.4%	1.47%	2.5	2.1%	50.8%	39.8%	56.0%	
Pregnancy outcomes				3	2.8%	75.9%	62.9%	81.0%	
outcomes				3.5	3.50%	91.7%	82.0%	94.6%	

QUVIVIQ® (daridorexant) Insomnia disorder ID-078A403 Version 4 23 October 2023, page 47/90

Confidential

Secondary outcome category ^a	Secondary outcome ^b	P _B (B, B1 and B2)	P _A ^c	Risk ratio	NI margin	Power for A vs B1	Power for A vs B2	Power for A vs B
_		62.0%	60.1%	2.5	93.00%	> 99.9%	>99.9%	> 99.9%
Pregnancy outcomes	Live birth ^{c,k}			3	124.00%	> 99.9%	>99.9%	> 99.9%
outcomes				3.5	155.00%	> 99.9%	> 99.9%	> 99.9%
.				2.5	16.5%	> 99.9%	> 99.9%	> 99.9%
Pregnancy outcomes	Premature birth ¹	11.0%	11.55%	3	22.0%	> 99.9%	> 99.9%	> 99.9%
outcomes				3.5	27.50%	> 99.9%	> 99.9%	> 99.9%
) () () () () () () () () () (2.10%	2.5	3.0%	39.5%	30.9%	43.7%

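### The margin comparison is described as rejecting that Cohort A's malformation rate is higher than B1's, but the test can only exclude an excess of 6 percentage points or more

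*Protocol*

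**What the plan says.** Protocol section 5.5.1 defines the test. "The null hypothesis is that P_A is larger than P_{B1} by a margin corresponding to a risk ratio of 3.0". With B1 assumed at 3%, the margin is 3% × 3.0 − 3% = 6 percentage points. The upper limit of the one-sided 97.5% interval for P_A − P_B1 is compared with that margin: "If the upper bound is below the NI margin, then noninferiority of A vs B1 will be concluded". The synopsis describes the same aim, ruling out a risk ratio of 3.0 or higher.

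Two other sentences attach a stronger conclusion:

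- Section 5.7.4.3 (internal comparator analysis) says the difference will be "compared to the defined clinical equivalence margin to reject the hypothesis that the rate in Cohort A is higher than in Cohort B1".
- Section 5.5.1, after Table 3, says that a prevalence in A below 3.15% would raise the power for this conclusion: "the rate of major congenital malformations in the infants of patients in Cohort A is not larger than in Cohort B1".

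The sentence in 5.7.4.3 follows one about secondary outcomes, but it refers to a single defined margin and names only Cohort B1. For secondary outcomes, section 5.5.2 and Table 4 give "power to rule out a difference represented by the risk ratios presented below", with margins at risk ratios of 2.5, 3 and 3.5 for each outcome.

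**The concern.** Rejecting an excess of 6 points or more is not the same as rejecting any excess. The first leaves every true difference between 0 and 6 points open. The second would need a margin of zero. The protocol sets up the first test and, in two places, describes its result as the second.

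This is the main safety conclusion of a pregnancy registry. If an author of the final report followed the wording of 5.7.4.3, a result that excludes only a tripling of malformations could be written up as showing no increase.

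**Working it through.** **Inputs (Protocol 5.5.1).** P_B1 = 3%; planned P_A = 3.15%; margin 0.06; one-sided α = 0.025; 102 outcomes in A and 204 in B1; stated power 80.1%.

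**Step 1: reproduce the plan's figure.** Use a Z-test on the difference with the variance from the size-weighted pooled rate and r = 2:

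- p̄ = (0.0315 + 2 × 0.03)/3 = 0.0305, so p̄(1 − p̄) = 0.02957.
- n_A = 1.5 × 0.02957 × (1.960 + 0.842)² / (0.06 − 0.0015)² ≈ 101.7, which rounds up to 102. n_B1 = 2 × 101.7, which rounds up to 204.
- SE = √[0.02957 × (1/102 + 1/204)] = 0.02085. Power = Φ(0.0585/0.02085 − 1.960) = Φ(0.845) = 80.1%.

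This matches the protocol. The formula as printed, with a simple mean of the two variances, gives 103/206 and 79.8% power at 102/204, which is close enough not to matter here.

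**Step 2: how often the margin is met when A's rate really is higher.** With unpooled variance, P(pass) = Φ[(0.06 − δ)/SE − 1.960], where δ = P_A − P_B1.

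- Risk ratio 1.5 (4.5% vs 3%): SE = √(0.045 × 0.955/102 + 0.03 × 0.97/204) = 0.02375. P = Φ(0.045/0.02375 − 1.960) = Φ(−0.065) = 47%.
- Risk ratio 2.0 (6% vs 3%): SE = √(0.06 × 0.94/102 + 0.03 × 0.97/204) = 0.02637. P = Φ(0.03/0.02637 − 1.960) = Φ(−0.822) = 21%.
- Risk ratio 3.0 (9% vs 3%): δ equals the margin, so P = Φ(−1.960) = 2.5%.

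Exact binomial enumeration of the upper limit gives the last two columns:

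| True risk ratio | Normal, unpooled | Exact, Wald limit | Exact, Newcombe limit |
|---|---|---|---|
| 1.05 (planned) | 79% | 76% | 53% |
| 1.5 | 47% | 51% | 29% |
| 2.0 | 21% | 27% | 12% |
| 3.0 | 2.5% | 5.1% | 1.6% |

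The pooled variance of Step 1 gives 52% and 24% at risk ratios of 1.5 and 2.0.

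**Step 3: an example.** Take 4/102 (3.9%) against 6/204 (2.9%), an observed risk ratio of 1.33. The Wald upper limit is 0.0098 + 1.960 × 0.02257 = 0.054. That is below 0.06, so noninferiority is concluded. The observed rate in A is nevertheless higher, and the interval includes excesses of up to 5.4 points.

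**Step 4: the sentence tested literally.** With a margin of zero and 102/204 outcomes, the chance of rejecting that A is higher is 2.5% at equal rates and 2.1% at the planned 3.15%. The study was not sized for that claim.

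**Step 5: dependence on the reference rate.** Keep the 6-point margin and use the normal, unpooled calculation. With B1 at 2%, the pass probabilities at risk ratios of 1.5 and 2.0 are about 73% and 45%. With B1 at 4% they are about 31% and 10%.

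**The case against.** The strongest reply is that the operative rule is already right. Section 5.5.1 states the null hypothesis with the margin and labels the conclusion noninferiority. The sentence in 5.7.4.3 mentions the margin, so it can be read as loose shorthand for that test. The sentence after Table 3 is a remark about power and not an analysis rule. The risk ratio and its interval will be reported as well (5.7.1.3), and section 8 asks for balanced reporting with limitations. All of this stands, and it makes the matter one of wording. It does not remove the contradiction: the analysis section names a hypothesis that the test does not address.

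Three stronger readings are tempting, and the protocol does not support them.

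- *The 2.5% error rate is breached.* True risk ratios of 1.5 and 2.0 lie inside the alternative of the stated test. Meeting the margin there is how any noninferiority design with this margin behaves. The percentages above would be error rates only against a zero-margin null, and the protocol sets up no such test.
- *The registry will report no increase, or the label will.* The only formal conclusion written down is noninferiority. What the report would claim beyond that is conjecture.
- *Secondary outcomes have a pass/fail rule with a margin still to be picked.* The placement of the sentence in 5.7.4.3 makes this possible to infer. But Table 4 is a power table across several risk ratios, much as Table 3 is for the primary outcome, and it sets no decision rule. The only margin tied to a decision is the 6 points in 5.5.1.

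**Conclusion.** The point holds as a wording error about what may be concluded. Section 5.7.4.3 and the sentence after Table 3 in 5.5.1 state a stronger conclusion than the test in 5.5.1 can give. Meeting the margin excludes an excess of 6 points or more and supports noninferiority within that margin, and nothing beyond that.

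The gap is large enough to matter. Under the Z/Wald approach, a true 50% increase would meet the margin about half the time and a true doubling in about one case in four or five. These figures assume 102/204 evaluable outcomes and B1 at 3%. They are lower with a Newcombe limit, and section 5.5.1 names the Z-test but no interval method. The design and the stated power are not in question on this point.

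**What to change.** 1. In section 5.7.4.3, replace the clause on the purpose of the margin comparison with: *to reject the hypothesis that the rate of major congenital malformations in Cohort A exceeds that in Cohort B1 by the NI margin (6 percentage points) or more; this does not show that the rate in A is not higher.* This also replaces the term clinical equivalence margin with the one margin that is defined.
2. In section 5.5.1, after Table 3, reword the end of the sentence on a lower observed prevalence to: *greater power to demonstrate noninferiority of Cohort A to Cohort B1 within the NI margin.*
3. State in 5.7.4.3 that this margin-based decision applies to major congenital malformations, and that the several margins per secondary outcome in Table 4 serve power only.

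No change is needed to the planned intervals or to the comparisons of secondary outcomes. The 102/204 outcomes, the enrollment targets and the 80.1% power stay as they are, and no new data are needed. The cost is a text amendment and a weaker permitted claim.
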